7.2 Investigations

7.2.1 Pregnancy Test

A urine pregnancy test is required for all females of childbearing potential at Visit 1. Women in natural or surgical post-menopause do not need to be tested for pregnancy at Visit 1.

7.2.2 Blood Pressure and Heart Rate

Blood pressure and heart rate will be measured at screening in supine position after 5-min rest. If blood pressure and heart rate are collected as part of Standard of Care on the same day of informed consent signing, then assessment taken prior to consent can be used. Blood pressure must be reassessed if screening and treatment are conducted on separate days.

7.2.3 Determination of CVAD Withdrawal and Infusion Functions

Withdrawal function will be determined by the following method:

- An empty 10mL graduated syringe will be attached to the catheter, forming an airtight seal. The syringe plunger will be pulled back to the 5 mL mark to attempt to withdraw blood. The CVAD is considered to have withdrawal function if at least 3 mL of blood (blood and any previously infused fluids) fills the syringe.

Infusion function will be determined by the following method:

- A 10-mL graduated syringe with 5 mL normal saline solution will be attached to the catheter to gently infuse the saline solution. The investigative site will be permitted to use saline from their own supply for the infusion function assessment. The CVAD is considered to have infusion function if the entire content of the syringe could be infused without significant resistance.

CVAD dysfunction, assessed for determining patient's eligibility, is defined as the inability to withdraw 3 mL of blood.

Restoration of CVAD function (patency), assessed for determining treatment efficacy, is defined by the two following actions:

- Ability to have 3 ml of blood (blood and any previously infused fluids) withdrawn
AND
- Ability to gently infuse 5 ml of saline

Therefore, restoration of CVAD function (patency) is assessed by first attempting to withdraw 3 ml of blood and if successful, then attempting to gently infuse 5 ml of normal saline solution. To further clarify, if the 3 ml of blood (blood and any previously infused fluids) cannot be withdrawn, the CVAD is considered as dysfunctional, and further assessments are required as per protocol [section 7.1.1](#) at the specified time points.

8. EFFICACY ASSESSMENTS

8.1 Primary Efficacy Variable

The primary efficacy variable is the percentage of subjects who have treatment success following a single instillation of study drug (CUSA-081, alteplase, or placebo) with a dwell

 Chiesi	Clinical Study Protocol
Clinical Study Code No.: CUSA-081-HEM-01	Version No.: 8.0
EUDRACT No./IND No.: 2019-002124-32/128551	Date: 21 FEB 2023

time up to 90 minutes. Treatment success is defined as the restoration of CVAD functionality measured as the ability to withdraw 3 mL of blood and infuse 5 mL of saline.

8.2 Secondary Efficacy Variables

The secondary variables of the study are as follows:

1. Percentage of subjects who have treatment success following a single instillation of study drug with a total dwell time up to 30 and 60 minutes;
2. Percentage of subjects who have treatment success after up to two instillations of study drug with a total dwell time up to 120, 150 and 180 minutes;
3. Rate of recurrent catheter dysfunction (defined as first re-occlusion) within 30 days following treatment with study drug.

9. SAFETY VARIABLES

The safety variables of the study are as follows:

- Treatment Emergent Adverse Events (TEAEs), Adverse Drug Reactions (ADRs), Serious Treatment Emergent Adverse Events (SAEs), serious related TEAEs, TEAEs leading to study withdrawal, and TEAEs leading to death
- Treatment Emergent Adverse Events of Special Interest (AESI), as defined in [Section 10.1](#)

10. ADVERSE EVENT REPORTING

10.1 Definitions

An **Adverse Event** is “any untoward medical occurrence in a patient or clinical trial subject administered a medicinal product and which does not necessarily have a causal relationship with this treatment”.

An adverse event can therefore be any unfavourable and unintended sign (including abnormal laboratory finding), symptom, or disease temporally associated with the use of a medicinal product, whether or not considered related to the medicinal product.

An **Adverse Drug Reaction** is an “untoward and unintended responses to an investigational medicinal product related to any dose administered”.

All adverse events judged by either the reporting Investigator or the Sponsor as having a reasonable causal relationship to a medicinal product qualify as adverse reactions. The expression “reasonable causal relationship” means to convey in general that there are facts (evidence) or arguments meant to suggest a causal relationship.

The definition covers also medication errors and uses outside what is foreseen in the protocol, including misuse and abuse of the product.

A. Serious Adverse Event (SAE)/Serious Adverse Drug Reaction is any untoward medical occurrence or effect that at any dose falls in one or more of the following categories:

- **Results in death**

Death is not an adverse event but an outcome. It is the cause of death that should be regarded as the adverse event. The only exception to this rule is “sudden death” where no cause has been

 Chiesi	Clinical Study Protocol
Clinical Study Code No.: CUSA-081-HEM-01	Version No.: 8.0
EUDRACT No./IND No.: 2019-002124-32/128551	Date: 21 FEB 2023

established; in this latter instance, “sudden death” should be regarded as the adverse event and “fatal” as its reason for being serious.

- **Is life-threatening**

Life-threatening refers to an event in which the subject was at risk of death at the time of the event (e.g., aplastic anemia, acute renal failure, and anaphylaxis). The term does not refer to an event which hypothetically might have caused death if it were more severe.

- **Requires hospitalization or prolongation of existing hospitalization**

Hospitalization refers to a situation whereby an AE is associated with unplanned formal overnight admission into hospital, usually for purpose of investigating and/or treating the AE. Hospitalization for the treatment of a medical condition that occurs on an “elective” or “scheduled” basis or for a pre-existing condition that did not worsen during the study should not necessarily be regarded as an AE. Complications that occur during the hospitalization are AEs. If a complication prolongs hospitalization, the event is an SAE. Emergency room visits that do not result in a formal admission into hospital should be evaluated for one of the other seriousness criteria (e.g., life-threatening; persistent or significant disability or incapacity; medically significant).

- **Results in persistent or significant disability or incapacity.**

The term significant disability should be viewed as any situation whereby an AE has a clinically important effect on the subject’s physical or psychological well-being to the extent that the subject is unable to function normally.

- **Is a congenital anomaly or birth defect**
- **Is a medically significant adverse event**

This criterion allows for any situations in which important adverse events/reactions that are not immediately life-threatening or do not result in death or hospitalization may jeopardize the subject’s health or may require intervention to prevent one of the above outcomes.

Examples of such events are intensive treatment in an emergency room or at home for allergic bronchospasm; blood dyscrasias or convulsions that do not result in hospitalisation; or development of drug dependency or drug abuse.

Medical and scientific judgment should be exercised in deciding whether an event is serious because medically significant.

Any suspected transmission via a medicinal product of an infectious agent is also considered a serious adverse reaction.

B. Non-Serious Adverse Event/Non-Serious Adverse Drug Reaction is an adverse event or adverse drug reaction that does not meet the criteria listed above for a serious adverse event/serious adverse drug reaction.’

C. Adverse Events of Special Interest (AESI): Adverse Events of Special Interest (AESI) will be collected from the time the subject is administered the first dose of study drug on Day 1 until the withdrawal of study drug (V1), and if spontaneously reported afterwards up until the 30 days ± 2 days follow up assessment

- I. Major bleeding (defined as severe blood loss [>5 mL/kg] or blood loss requiring transfusion or causing hypotension requiring use of inotropic agents),

 Chiesi	Clinical Study Protocol
Clinical Study Code No.: CUSA-081-HEM-01	Version No.: 8.0
EUDRACT No./IND No.: 2019-002124-32/128551	Date: 21 FEB 2023

- II. Embolism
- III. Thrombosis
- IV. Catheter related blood stream infections (CRBSI).

10.2 Expectedness

An expected adverse reaction is an adverse reaction, the nature or severity of which is consistent with the applicable reference safety information (Investigator's Brochure for CUSA-081), otherwise it is considered unexpected.

Reports which add significant information on specificity or severity of a known, already documented serious adverse drug reaction constitute unexpected events. For example, an event more specific or more severe than described in the Investigator's Brochure would be considered as "unexpected". Examples of such events are: (a) acute renal failure as a labelled ADR with a subsequent new report of interstitial nephritis and (b) hepatitis with a first report of fulminant hepatitis

In the event an exacerbation is interpreted as due to lack of efficacy, it should not be classified as drug related.

10.3 Intensity of Adverse Event

Each Adverse Event must be rated on a 3-point scale of increasing intensity:

- **Mild:** The event causes a minor discomfort or does not interfere with daily activity of the subject or does not lead to either modification of test treatment dosage or establishment of a correcting treatment.
- **Moderate:** The event perturbs the usual activity of the subject and is of a sufficient severity to make the subject uncomfortable. The event leads to a diminution of dosage of the test treatment, or a temporary interruption of its administration or to the establishment of a correcting treatment.
- **Severe:** The event prevents any usual routine activity of the subject and causes severe discomfort. It may be of such severity to cause the definitive interruption of test treatment.

10.4 Causality Assessment

The following "binary" decision choice will be used by the Investigator to describe the causality assessment:

- Reasonable possibility of a relatedness
- No reasonable possibility of relatedness

The expression "reasonable possibility of relatedness" is meant to convey, in general, that there are facts (evidence) or arguments meant to suggest a causal relationship.

The Investigator will be asked to consider the following before reaching a decision on causality assessment:

- Time relationship between study drug intake and event's onset;
- Dechallenge (did the event abate after stopping drug?);
- Rechallenge (did the event reappear after reintroduction?);
- Medical history;
- Study treatment(s);

 Chiesi	Clinical Study Protocol
Clinical Study Code No.: CUSA-081-HEM-01	Version No.: 8.0
EUDRACT No./IND No.: 2019-002124-32/128551	Date: 21 FEB 2023

- Mechanism of action of the study drug;
- Class effects;
- Other treatments-concomitant or previous;
- Withdrawal of study treatment(s);
- Lack of efficacy/worsening of existing condition;
- Erroneous treatment with study medication (or concomitant);
- Protocol related process.

10.5 Action Taken with the Study Drug Due to an AE

- Dose not changed
- Drug permanently withdrawn
- Not applicable

10.6 Other Actions Taken

- Specific therapy/Medication
- Concomitant Procedure
- Not applicable

10.7 Outcome

Each Adverse Event must be rated by choosing among:

- Recovered/resolved
- Recovering/resolving
- Not recovered/not resolved
- Recovered with sequelae/resolved with sequelae
- Fatal
- Unknown

10.8 Recording Adverse Events

All Adverse Events occurring during the course of the study must be documented in the Adverse Event page of the electronic Case Report Form (eCRF). If the Adverse Event is considered serious or meets the definition of AESI, the Adverse Event Form in the eCRF must also be completed.

It is responsibility of the Investigator to collect all adverse events (both serious and non-serious) derived by spontaneous, unsolicited reports of subjects, by observation and by routine open questionings.

The recording period for Adverse Events is the period starting from the Informed Consent signature until the subject's study participation ends.

Clinically significant abnormalities detected at Visit 1 not due to a pre-existing condition or clinically significant changes at the following visits in the medical opinion of the investigator must be reported as adverse events in the eCRF.

If a clinically significant abnormal laboratory finding or other abnormal assessment meets the definition of an AE, then the AE eCRF page must be completed, as appropriate. A diagnosis, if known, or clinical signs and symptoms if diagnosis is unknown, rather than the clinically

 Chiesi	Clinical Study Protocol
Clinical Study Code No.: CUSA-081-HEM-01	Version No.: 8.0
EUDRACT No./IND No.: 2019-002124-32/128551	Date: 21 FEB 2023

significant abnormal laboratory finding, should be reported on AE eCRF page. If no diagnosis is known and clinical signs and symptoms are not present, then the abnormal finding should be recorded.

For pharmacovigilance purposes, all SAEs and AESIs should be followed-up in order to elucidate as completely and practically as possible their nature and/or causality until resolution of all queries, clinical recovery is complete, laboratory results have returned to normal, stable condition is reached or until the subject is lost to follow-up. Follow-up may therefore continue after the subject has left the study. In this case, the follow-up will continue with no timelines for related SAEs and AESIs, while for unrelated SAEs and AESI the type and extent of follow-up undertaken will be determined for each individual case and will depend upon the nature (e.g. events with poor prognosis or which do not resolve), severity and medical significance of the event.

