⁴ The Day 30 (\pm 2 days) follow-up assessment will occur via phone or may occur in person if the subject has a scheduled clinic visit. The follow-up period is calculated from the date of the randomization/treatment Day.

⁵ A urine pregnancy test is required for all females of childbearing potential. Women in natural or surgical post-menopause do not need to be tested for pregnancy.

⁶ Only concomitant medications and/or procedures ongoing at the time of consent, or stopped within 30 days prior to informed consent, and only new concomitant medications and/or procedures related to spontaneously reported SAEs/AESIs will be collected after randomization.

⁷ Note that all catheter assessments are based on the dwell time from the time of study drug instillation (i.e., from "0 min"; NOT from the time of the prior assessment). All efforts should be made to conduct the assessment at the required time point. The window of \pm 5 minutes is also from the time of study drug instillation and not time of the prior assessment. Assessments of catheter dysfunction are described in Sections [7.1.1](#) and [7.2.3](#). In the event a 2nd dose of study drug is needed, it should be administered within 15 min of withdrawal of the 1st dose from the CVAD.

⁸ Once CVAD function has been restored (i.e. the ability to both withdraw at least 3 mL of blood and infuse 5 mL of saline solution), the subject will be deemed a Treatment Success and will exit the treatment algorithm (

	Clinical Study Protocol
Clinical Study Code No.: CUSA-081-HEM-01	Version No.: 8.0
EUDRACT No./IND No.: 2019-002124-32/128551	Date: 21 FEB 2023

Figure 1). Therefore, subsequent dosing and catheter function checks will not be performed during V1. At 180 minutes, or in the case of Early Withdrawal, if treatment success is not achieved, any subsequently administered standard of care and related outcome will be documented.

⁹ Assessment of recurrent catheter dysfunction as described in [Section 7.1.2](#). Information including, but not limited to, the need for other thrombolytic administration and/or catheter removal or replacement will be collected beyond study drug administration and up through Day 30 (\pm 2 days). Subjects will be requested to document the date of re-occlusion and any intervention or the date the catheter was removed in order to provide the data when contacted by site personnel.

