Subjects will exit the treatment algorithm when treatment success is achieved at the specified time points, or after assessment of CVAD function 90 minutes following the second instillation of study drug (time point 180 min), whichever occurs first. Once a subject exits the treatment algorithm, assessments of CVAD function are completed for Day 1. In unsuccessful cases, further treatments for restoration of catheter functionality may be provided per the site's standard of care for CVAD. At 180 minutes, or in the case of Early Withdrawal, if treatment success is not achieved, any subsequently administered standard of care and related outcome will be documented.

Subjects will be monitored for AEs (including SAEs and AESIs) during the treatment period (Day 1) from the time the subject is administered the first dose of study drug until the withdrawal of study drug at V1, and for spontaneously reported SAEs and AESIs afterwards up until the Day 30 (± 2 days) follow up assessment.

Concomitant medications and procedures will also be collected as part of the SAE reporting requirements.

At the end of Visit 1, subjects will be discharged with instructions on how to record and report the status of their CVAD during the 30-day follow-up period, including:

- Date of first recurrent catheter re-occlusion (for those with treatment success at V1),
- Date and type of any additional treatment they received for catheter dysfunction, and
- Date of catheter removal or replacement.

7.1.2 Visit 2

The Day 30 (± 2 days) follow-up assessment will occur by phone or in person if the subject has a scheduled clinic visit. Spontaneously reported SAEs, AESIs, and related concomitant medications will be recorded and the status of the CVAD function will be determined by asking the subject to respond to the questions provided at the V1 discharge.

 Chiesi	Clinical Study Protocol
Clinical Study Code No.: CUSA-081-HEM-01	Version No.: 8.0
EUDRACT No./IND No.: 2019-002124-32/128551	Date: 21 FEB 2023

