Table 14.3.1.2.12	Post-Treatment Emergent Adverse Events by System Organ Class, Preferred Term and Maximum Severity (Safety Set)	AET005	The number of events (“E”) columns will not be displayed.	Source: Listing 16.2.7.11  Footnotes: [1] System Organ Class and Preferred Term are coded using MedDRA Version xx.x [2] If a subject reports the same AE more than once within that SOC/PT, the AE with the maximum severity will be counted.
Table 14.3.1.2.13	Serious Post-Treatment Emergent Adverse Events by System Organ Class and Preferred Term (Safety Set)	AET003		Same as Table 14.3.1.2.11
Table 14.3.1.2.14	Non-Serious Post-Treatment Emergent Adverse Events by System Organ Class and Preferred Term (Safety Set)	AET003		Same as Table 14.3.1.2.11
Table 14.3.1.2.15	Post-Treatment Emergent Adverse Drug Reactions by System Organ Class and Preferred Term (Safety Set)	AET003		Same as Table 14.3.1.2.11
Table 14.3.1.2.16	Serious Post-Treatment Emergent Adverse Drug Reactions by System Organ Class and Preferred Term (Safety Set)	AET003		Same as Table 14.3.1.2.11
Table 14.3.1.2.17	Severe Post-Treatment Emergent Adverse Events by System Organ Class and Preferred Term (Safety Set)	AET003		Same as Table 14.3.1.2.11
Table 14.3.1.2.18	Non-Serious Post-Treatment Emergent Adverse Events Reported in $\geq 5\%$ of Subjects in Any Treatment Arm by System Organ Class and Preferred Term (Safety Set)	AET003	If there is no PT within the SOC then the SOC will not be displayed.	Same as Table 14.3.1.2.11

Table Number	Table Title	Template Code	Notes	Footnotes/Source Listing Number
Table 14.3.2.1	Treatment Emergent Adverse Events of Special Interest by Category (Safety Set)	AET006	Data to display for each category: 
 
- Number of Subjects with at Least One Event, Percentage of subjects in the relevant treatment period with at least one event, number of events, 95% CI for the percentage
 
- AESI categories: 
 
- Any AESI
 
- Major Bleeding
 
- Embolism
 
- Thrombosis
 
- Catheter Related Blood Stream Infection (CRBSI)
 
 
 
	Source: Listing 16.2.7.8  Footnotes: [1] 95% CIs are the exact binomial confidence intervals for the percentage of subjects experiencing at least one event.

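### The protocol sets a narrower, passive adverse event rule after Visit 1 in Section 7.1 and a full, active one in Section 10.8, so the SAP's post-treatment tables may understate non-serious event rates

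*Protocol*

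**What the plan says.** **Narrower rule.** Protocol Section 7.1.1 has subjects monitored for all adverse events on Day 1 until study drug is withdrawn, "and for spontaneously reported SAEs and AESIs afterwards up until the Day 30 (± 2 days) follow up assessment". For the Day 30 contact, Section 7.1.2 says "Spontaneously reported SAEs, AESIs, and related concomitant medications will be recorded". Non-serious events are not named in either place. Section 10.1 applies the same passive approach to AESIs after Visit 1 ("and if spontaneously reported afterwards up until the 30 days ± 2 days follow up assessment"). Footnote 6 of the study schedule (Table 7) is in line with it: "only new concomitant medications and/or procedures related to spontaneously reported SAEs/AESIs will be collected after randomization".

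**Broader rule.** Section 10.8 states: "It is responsibility of the Investigator to collect all adverse events (both serious and non-serious) derived by spontaneous, unsolicited reports of subjects", and adds observation and routine open questions as sources. On timing it says "The recording period for Adverse Events is the period starting from the Informed Consent signature until" the end of the subject's participation, which includes the 30-day follow-up.

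**Analysis.** Protocol Section 12.3.6 plans a summary of post-treatment events over the 30-day follow-up without limiting it to SAEs or AESIs. SAP Section 10.2 defines a post-treatment event as any event starting after the treatment period and repeats the adverse event tables for these events. SAP Section 16.1 includes Table 14.3.1.2.14, "Non-Serious Post-Treatment Emergent Adverse Events by System Organ Class and Preferred Term (Safety Set"), and Table 14.3.1.2.18, which shows non-serious post-treatment events reaching 5% in any arm. No footnote mentions limited ascertainment, and SAP Section 12 does not raise the point.

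**The concern.** A site working from the visit instructions in Section 7.1 would not ask about non-serious events after Visit 1 and would have no instruction there to record them. A site working from Section 10.8 would ask and record. Both would be following the protocol. The resulting data go into the same tables, and the reader of those tables has no means of knowing which practice lies behind a count.

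What is at stake is the description of tolerability after Day 1, part of the fifth secondary objective. A low or zero count of non-serious post-treatment events would read as good tolerability when it may only reflect that nobody asked. The primary efficacy comparison is not touched.

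**Working it through.** The plan states no figure on this point, so there is none to reproduce. The check is a comparison of texts, followed by two calculations for scale.

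**1. The two rules side by side, from the end of Visit 1 to Day 30**

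| | Sections 7.1.1, 7.1.2 | Section 10.8 |
|---|---|---|
| SAEs | in scope | in scope |
| AESIs | in scope (also 10.1, 10.9) | in scope |
| Other non-serious events | not named | in scope |
| Method | spontaneous report | spontaneous report, observation, open questions |

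For SAEs and AESIs only the method differs. For other non-serious events the scope differs as well.

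**2. Does another passage settle it?** No. The schedule marks adverse events at Visit 2 but does not say which kinds. Footnote 10 gives the start of collection and the follow-up of ongoing events, not whether new non-serious events are collected after Visit 1.

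**3. Tables affected.** Tables 14.3.1.2.11 (all events), .12 (by maximum severity), .14 (non-serious), .15 (drug reactions), .17 (severe) and .18 (non-serious, 5% threshold) can all contain non-serious events. Tables .13 and .16 hold serious events only and are not affected in scope.

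**4. Length of the window.** The SAP ends the treatment period at the assessment where patency is achieved or at the 180-minute assessment. With exit at 30 minutes the share of a 30-day follow-up is 30/(30 × 24 × 60) = 0.07%. With a second instillation given 15 minutes after withdrawal of the first, it is (90 + 15 + 90)/43,200 = 195/43,200 = 0.45%. The disputed window is thus at least 99.5% of follow-up time. This is a share of time, not of events.

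**5. Illustration of the effect on a tabulated rate.** Let p be the true incidence, f the share of subjects at sites that ask openly, and s the fraction captured elsewhere. All three are assumptions. Then

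tabulated incidence = p × [f + (1 − f) × s].

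For p = 6%:
- f = 1: 6.0%
- f = 0.5, s = 0.5: 6% × 0.75 = 4.5%
- f = 0.5, s = 0: 6% × 0.5 = 3.0%
- f = 0, s = 0 to 0.5: 0% to 3.0%

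**6. Effect on the 5% table.** At the planned arm sizes of 473, 53 and 315, the threshold is 24, 3 and 16 subjects. The binomial chance that an arm reaches it is:

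| Tabulated incidence | CUSA-081 | Placebo | Alteplase | Any arm |
|---|---|---|---|---|
| 6% | 83% | 62% | 79% | 99% |
| 3% | 1% | 21% | 3% | 24% |

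The last column assumes the same incidence in each independent arm: 1 − (0.173 × 0.376 × 0.213) = 0.986 and 1 − (0.990 × 0.788 × 0.970) = 0.243. The study stopped early, so actual arms may be smaller and these chances will differ.

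**The case against.** The best reply is that this is a narrow instruction beside a broad one, not a pair of opposites. A reader might infer that a site cannot obey both. The text does not support that: Section 7.1.1 does not forbid recording non-serious events, and a site that follows Section 10.8 also captures every SAE and AESI named in Section 7.1. This stands. The difficulty is that a site following Section 7.1 alone falls short of Section 10.8.

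A reader might also infer that the tables will mix complete and incomplete data. That is not established. One final eCRF served the trial, and it or the monitoring plan may have imposed a single practice; neither is available here. If every site followed 10.8 the tables are complete, and if every site followed 7.1 they are uniformly incomplete. Mixing needs sites to differ, which is possible across about 100 of them but not shown.

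Three further points also stand. The time share in step 4 does not mean that almost all safety information is compromised, since SAEs and AESIs are in scope throughout. The declared safety variables are treatment-emergent and so precede the disputed window. An event below 5% is not hidden, because Tables 14.3.1.2.11 and .14 have no threshold and Listing 16.2.7.11 covers all post-treatment events.

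None of this helps with events that were never recorded. No threshold-free table or listing can show those.

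**Conclusion.** The inconsistency is in the current protocol and should be resolved. It is confined to non-serious, non-AESI events between the end of the Day 1 treatment period and Day 30; for SAEs and AESIs only the method of ascertainment is in doubt. The consequence is that the absolute rates of such events in Tables 14.3.1.2.11, .12, .14, .15, .17 and .18 may be too low, and that low or zero counts cannot be told apart from non-collection.

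The size cannot be estimated from the documents. The 6% to 3% example rests wholly on assumed incidence, site split and capture. A reader might infer a bias between treatments. The documents point the other way: site staff other than the pharmacist are blinded, so under-capture should on average be similar across arms. Efficacy conclusions are unaffected.

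**What to change.** **Where collection is still possible:** reconcile Protocol Sections 7.1.1, 7.1.2, 10.1 and 10.8 and schedule footnotes 6 and 10 to one ascertainment rule that matches the planned tables. One way is a standard open adverse event question, put to every subject at the Day 30 contact. The contact already exists, so the cost is wording and one question.

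**For data already collected:** SAP Section 12 says the study was terminated early, so completed contacts cannot be changed but reporting can.
- State in the SAP or study report which rule the eCRF and the sites applied after Visit 1.
- Keep every recorded event in the tables and listings.
- Footnote Tables 14.3.1.2.14 and .18 as based on possibly incomplete ascertainment of non-serious events, and carry the note to .11, .12, .15 and .17, which include such events.

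The tables should not be deleted or cut down to SAEs and AESIs. That would drop observed safety data, including non-serious drug reactions, and would conflict with Protocol Section 12.3.6 and with SAP Section 7.11.1, under which all collected data are used. The cost is one statement and a footnote.
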